9.4 Product Use Pattern Categories/Product Adherence

Summary Table of Product Use	
Population	: 
 • As Exposed Set 
 ➤ Product use pattern categories • Per Protocol Set
Contents	: Refer to Descriptive statistics
Analysis variables	: 
 • For cigarettes 
 ➤ Days of exposure to cigarettes [days] ➤ Daily product consumption (cigarettes)[/day] • For IQOS 
 ➤ Days of exposure to IQOS [days] ➤ Daily product consumption (IQOS) [heatsticks/day] • For heat-not-burn other than IQOS 
 ➤ Days of exposure to heat-not-burn other than IQOS [days] ➤ Daily product consumption (heat-not-burn other than IQOS) [/day] • For e-cigarettes 
 ➤ Days of exposure to e-cigarettes [days] ➤ Daily product consumption(e-cigarettes) [/day] • For smokeless tobacco pipe 
 ➤ Days of exposure to smokeless tobacco pipe [days] ➤ Daily product consumption smokeless tobacco pipe [/day] • For smokeless tobacco product 
 ➤ Days of exposure to smokeless tobacco pipe [days] ➤ Daily product consumption smokeless tobacco pipe [/day] • For cigar/ pipe/ kiseru/ shisha 
 ➤ Days of exposure to cigar/ pipe/ kiseru/ shisha [days] ➤ Daily product consumption (cigar/ pipe/ kiseru/ shisha) [/day] • For nicotine replacement therapy 
 ➤ Days of exposure to nicotine replacement therapy [days]

Confidentiality Statement

Data and information contained in this document are considered to constitute trade secrets and confidential commercial information, and the legal protections provided to such trade secrets and confidential information are hereby claimed under the provisions of applicable law. No part of this document may be publicly disclosed without the written consent of Philip Morris Products S.A

Summary Table of Product Use	
	➤ Daily product consumption (nicotine replacement therapy) [/day]
Target visit	Overall for the summary table, month 1 to 6 and overall for listing.
Output	15.2.4.1 Summary Table of Product Use Categories - As Exposed Set, Per Protocol Set - 15.3.4.1 Listing of Product Use Categories - As Exposed Set -

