### 12.3 Product use

[figure not shown]
Although patients are being requested to use solely the product allocated to their respective study arm, it is considered that not all patients randomized to the IQOS arm or to continue smoking cigarettes will exclusively use the randomized product at all times during the study. Patients may concomitantly use IQOS and cigarettes (dual-use). To assess dual use of IQOS and cigarettes, PMI has defined categories of pattern of product use.

Product use pattern categories will be specified based on the average number of product used per month of each category (i.e., Marlboro HeatSticks or smoked cigarettes) as self-reported in the product use questionnaire over the study duration. Further determinants, such as percentages of the respective products, or numbers of other nicotine-containing products may be used, and will be provided in the SAP.

Actual product use pattern categorization is described in Figure 3. Primary analysis will consider only those patients who used only HeatSticks and/or cigarettes. Those who used other nicotine-containing products (e.g., e-cigarettes) will be considered in a separate category, "Other" (not represented in Figure 3). More granular product exposure categories may be used for the detailed description of the product use patterns observed in the study. Full details of the product use categories will be reported in the SAP.

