## **12.7 Secondary Analysis**

The analysis of PD at 3 months, CAL at 3 and 6 months will be also performed, as a secondary endpoint.

There will be an adjustment for multiplicity for the secondary testing of CAL and PD within the As Exposed Set as defined in section 12.1.5.

Urinary NEQ, total NNAL and CEMA levels (concentration data adjusted for creatinine will be analyzed on a logarithmic scale) using an MMRM with the BoExp geometric mean value as the dependent variable, adjusting for daily cigarette consumption at baseline and sex, visit, baseline BoExp level, exposure group and its interaction with visit. Site will be included as a random effect. The modeling assumptions will be evaluated similar to that in the primary analysis.

Descriptive statistics for the BoExp will be summarized at each visit by exposure group and overall (across all patients). The primary endpoint will also be summarized by strata (daily cigarette consumption and sex).

The other secondary endpoints will be summarized descriptively at each visit by exposure group and overall (across all patients) in the As Exposed Set (unless otherwise defined):

- Change in mean full-mouth PD.
- Change in mean full-mouth CAL.
- Mean PD change in sites with initial PD < 4 mm, and with initial PD of 4 mm to < 5mm, 5 mm to < 6 mm, 6 mm to < 7 mm and  $\geq$  7 mm.

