3.2 Secondary Objectives and Endpoints

The secondary objectives of this study are:

1. To evaluate the effect of switching to IQOS use compared to continued cigarette smoking on the response of PD and clinical attachment level (CAL) to mechanical periodontal therapy over time.

Endpoints (3 and 6 months):

- Mean PD change in sites with initial PD ≥ 4 mm after mechanical periodontal therapy (3 month only).
- Mean CAL change in sites with initial PD ≥ 4 mm after mechanical periodontal therapy (3 and 6 months).

2. To evaluate the differences of periodontal parameters in the response to periodontal therapy in patients who switch to IQOS use compared to those who continue to smoke cigarettes.

Endpoints (3 and 6 months):

- Change in mean full-mouth CAL
- Change in mean full-mouth PD
- Mean PD change in sites with initial PD < 4 mm, and with initial PD of 4 mm to < 5 mm, 5 mm to < 6 mm, 6 mm to < 7 mm and ≥ 7 mm
- Mean CAL change in sites with initial PD < 4 mm, and with initial PD of 4 mm to < 5 mm, 5 mm to < 6 mm, 6 mm to < 7 mm and ≥ 7 mm
- Change in the number of sites with PD < 4 mm, with PD 4 mm to < 5 mm, with PD 5 mm to < 6 mm, with PD 6 mm to < 7 mm and with PD ≥ 7 mm
- Change in gingival index (GI) score
- Change in tooth mobility (grade)

Confidentiality Statement

Data and information contained in this document are considered to constitute trade secrets and confidential commercial information, and the legal protections provided to such trade secrets and confidential information are hereby claimed under the provisions of applicable law. No part of this document may be publicly disclosed without the written consent of Philip Morris Products S.A

- Change in plaque control record (PCR)
 - Change in bleeding on probing (BOP) scores
3. To evaluate the levels of biomarkers of exposure (BoExp) over the exposure period in patients who switch to IQOS use and patients who continue to smoke cigarettes.

Endpoint (3 and 6 months):

- Urinary nicotine equivalents (NEQ), total 4-[methylnitrosamino]-1-[3-pyridyl]-1-butanol (NNAL) and 2-cyanoethylmercapturic acid (CEMA).
4. To describe self-reported tobacco or nicotine containing product use over the duration of the study in patients switching to IQOS use and patients who continue to smoke cigarettes.

Endpoint:

- Number of self-reported tobacco or nicotine containing product use
5. To monitor safety.

Endpoint:

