5.2 Product Use

The number of Cigarettes, Heatsticks, and other nicotine/tobacco containing product used daily, as reported by the patient and collected in the electronic diary, will be used to monitor product use and evaluate adherence to product allocation.

Patients will be classified according to their monthly actual product use pattern into four categories: cigarette users; IQOS user, dual user, or other as described in Figure 2. “Other” will include the following products: Other heat not burn products, e-cigarettes, Smokeless Tobacco Pipe, Smokeless Tobacco, Cigars/Pipes/Kiseru/Shisha, and Nicotine Replacement Therapy.

The calculation of the monthly product use to classify patients into the four categories is described in section 5.2.3

Confidentiality Statement

Data and information contained in this document are considered to constitute trade secrets and confidential commercial information, and the legal protections provided to such trade secrets and confidential information are hereby claimed under the provisions of applicable law. No part of this document may be publicly disclosed without the written consent of Philip Morris Products S.A

[figure not shown]

Figure 2: Product Use Categories

Abbreviations: HS, Marlboro HeatSticks; cig, cigarette

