8 ANALYSIS SETS

The main population for non-safety analysis will be the As Exposed Set. Safety will be analyzed using the Safety Set.

As this study was intended to investigate the effects of IQOS and/or cigarettes on periodontitis treatment, therefore patients who are not in the cigarette, IQOS or dual-user product use categories will not be analyzed except in the Safety Set described below. There is no systematic way to quantify product use for patients who were using other products and the effects of these products on periodontitis are not known. Furthermore, this study was not powered to assess the impact of other products on periodontitis.

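### Secondary objective 4 (product use over the study) is only partly answered: one whole-study table, with users of other nicotine products excluded by SAP section 8

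*SAP*

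**What the plan says.** Secondary objective 4 is "To describe self-reported tobacco or nicotine containing product use over the duration of the study", in patients who switch to IQOS and patients who go on smoking. Its endpoint is "Number of self-reported tobacco or nicotine containing product use" (SAP section 3.2).

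Protocol section 12.7 gives the reporting rule: "The other secondary endpoints will be summarized descriptively at each visit by exposure group and overall (across all patients) in the As Exposed Set", subject to a caveat that allows another definition. Its list includes the number of tobacco or nicotine products used. It then adds supportive analyses on the FAS, Per Protocol and Adherent Use populations.

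The SAP delivers one consumption table: "15.2.4.1 Summary Table of Product Use Categories - As Exposed Set, Per Protocol Set". Its timing is "Overall for the summary table, month 1 to 6 and overall for listing". The matching listing, 15.3.4.1, is on the As Exposed Set. The table has rows for cigarettes, HeatSticks and six other product classes, each with days of exposure and daily consumption.

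On who is included, SAP section 5.2 says: "Patients will be classified according to their monthly actual product use pattern into four categories" (cigarette, IQOS, dual and Other). The opening of SAP section 8 says that "patients who are not in the cigarette, IQOS or dual-user product use categories will not be analyzed except in the Safety Set described below". Protocol section 12.3 says of users of other products: "Those who used other nicotine-containing products (e.g., e-cigarettes) will be considered in a separate category".

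SAP section 7 declares two changes from the protocol: the major-deviation rule for the As Exposed Set, and the removal of the Adherent Use Set.

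**The concern.** The primary comparison is by actual product use, not by randomised arm. How a reader judges it depends on who used what, in which arm and when. Objective 4 is where the report should show that.

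As planned, the summary has three gaps. It has no time dimension, so a return to cigarettes late in the study looks the same as a late switch away from them. It leaves out the patients who used e-cigarettes, other heated tobacco or nicotine replacement, although it prints rows for those products. It shows use by randomised arm only in the Per Protocol Set, so the 10% non-adherence assumed in the sample size cannot be checked in all randomised patients.

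**Working it through.** The plan states no figure to reproduce for this endpoint, so the check is mainly of text against text.

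**1. Timing.** Protocol section 12.7 asks for visit-level summaries; SAP section 9.4 gives the table an overall value only. SAP section 5.2.2 defines daily consumption as total consumption divided by the days from randomisation to the last monthly report. To see what is lost, take two assumed patients over six 30-day months:

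- Patient A smokes 0 cigarettes/day in months 1 to 3 and 20/day in months 4 to 6: (0 × 90 + 20 × 90) / 180 = 10/day.
- Patient B smokes 20/day in months 1 to 3 and 0 in months 4 to 6: (20 × 90 + 0 × 90) / 180 = 10/day.

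If days of exposure means days on which the product was used (the SAP does not define it), both also show about 90 days. The table cannot tell them apart. Up to V3 their averages are 0 and 20/day. SAP section 5.2.5 does derive average cigarette use at V3 and V4, and the primary model uses average daily cigarette use at each visit as a covariate, but no listed output tabulates it. That derivation is cumulative, so at V4 both patients are back at 10/day.

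**2. Other users.** The steps are:

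- SAP section 5.2 assigns six product classes to Other.
- The opening of SAP section 8 confines patients outside the cigarette, IQOS and dual categories to the Safety Set.
- Table 15.2.4.1 is on the As Exposed and Per Protocol Sets, and Listing 15.3.4.1 is on the As Exposed Set.
- No product-use output is on the Safety Set.

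Consumption by Other users therefore appears in no table or listing, and the rows for the six other classes are likely to be empty or nearly so. The reasons in section 8 do not fit a descriptive endpoint. Unknown effects on periodontitis and lack of power concern efficacy. The remaining reason, that use of these products cannot be quantified systematically, conflicts with SAP sections 5.2.1 to 5.2.3, which define total, daily and monthly consumption for them.

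**3. Randomised arm.** Protocol section 12.7 calls for a supportive FAS analysis; SAP section 9.4 has none for product use. The Per Protocol table is by randomised product (SAP sections 8.3 and 9.1.3.1). Table 15.2.2.2 covers all randomised patients by use category, but it reports analysis-set membership, not consumption.

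**4. Declaration.** Neither of the two changes in SAP section 7 covers the dropped visits, the missing FAS version or the exclusion of Other users.

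**5. A copy error.** Under smokeless tobacco product, SAP section 9.4 repeats the two smokeless tobacco pipe variables.

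**The case against.** A reader might infer that objective 4 cannot be answered at all. The documents do not support that. The objective is limited to IQOS switchers and continuing smokers, and its endpoint names no time points, whereas objectives 2 and 3 name 3 and 6 months. The table covers cigarette, IQOS and dual users, and the listing keeps their monthly data. Protocol section 12.7 itself makes the As Exposed Set the main set for this endpoint. Its list also includes adverse event incidence, which does not fit a literal visit-by-visit rule. Total NNAL and CEMA are summarised at baseline, V3 and V4 by use category, which gives indirect evidence on returning to cigarettes.

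A reader might also infer that the other-product rows are zero by construction. That cannot be shown. The rule for entering Other sits in Figure 2, which could not be read here. SAP sections 8.1 and 8.3 do not exclude Other users. The primary analysis states its own restriction to three categories, which would be redundant if the As Exposed Set already had it. SAP section 5.2.4 leaves other products out of the dual-user percentages, which suggests that some categorised patients may use them a little.

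Nor does the averaging hide everything. Someone at 10/day throughout and someone at 20/day for half the study share an average, but on the reading above they show about 180 and 90 days of exposure. Only the timing is lost.

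These points narrow the concern. They do not supply a summary over time, consumption data for Other users, or use by arm in the FAS. Section 8 does state its exclusion openly, but section 7 does not list it as a change.

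**Conclusion.** Objective 4 is partly answered. For cigarette, IQOS and dual users the report would give a whole-study average, days of exposure and a monthly listing. Missing are any tabulated change in use over time, any consumption data for Other users, and use by randomised arm outside the Per Protocol Set. The first and third gaps depart from protocol section 12.7, and the second departs from its call for a summary across all patients. None is declared in SAP section 7.

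The conclusion assumes that the opening of SAP section 8 governs the sets defined below it; if it does not, the second gap closes and the other two remain. The documents give no rate of other-product use, so the number of patients affected cannot be stated. No inferential result depends on this table. It should nevertheless be corrected, because the primary result is read by actual use.

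**What to change.** - Produce Table 15.2.4.1 by month (1 to 6) and overall, or at least at V3 and V4 and overall. Monthly figures are better, because a cumulative V4 average only repeats the whole-study value.
- Run it on the FAS or on all randomised patients with product-use data, by randomised arm and by use category with an Other column.
- Run Listing 15.3.4.1 on the same patients.
- State in SAP section 8 that its exclusion of Other users does not apply to this descriptive endpoint.
- Declare in SAP section 7 any departure from protocol section 12.7 that remains.
- Correct the repeated smokeless tobacco variables.

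The cost is SAP and table-shell wording plus a little programming. The monthly questionnaire data are already collected, and no patient procedure changes.

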9.5 Endpoint Evaluation

9.5.1 Primary Analyses

The primary study hypothesis is that there will be a favorable difference in the mean PD at 6 months in IQOS users as compared to smokers who continue to smoke cigarettes in patients with generalized chronic periodontitis.

9.5.1.1 Primary Analyses

Primary Analysis of Change from Baseline in PD at V4	
Population	
 • As Exposed Set For this analysis, subjects categorized in IQOS user, cigarette user or dual user will be included with initial PD \geq 4mm will be included.
	The primary analysis will be performed on the As Exposed Set using a mixed model for repeated measurements (MMRM). Estimates of difference in PD will be calculated for Cigarette User against IQOS User categories and Cigarette User against Dual User categories. The model will include the PD change from baseline as the dependent variable, adjusting for the following covariates; 
 1. Daily cigarette consumption at V1 2. Disease severity at V1 3. Full mouth PD at V1 4. Visit 5. Product use pattern (IQOS user, cigarette smoker or dual user) 6. Interaction between visit and product use

Confidentiality Statement

Data and information contained in this document are considered to constitute trade secrets and confidential commercial information, and the legal protections provided to such trade secrets and confidential information are hereby claimed under the provisions of applicable law. No part of this document may be publicly disclosed without the written consent of Philip Morris Products S.A

Primary Analysis of Change from Baseline in PD at V4

7. Average daily cigarette use at each visit
8. Interaction between Daily cigarette consumption at V1 and product use
9. Interaction between Disease severity at V1 and product use
10. Time since last SRP
11. Number of target tooth/teeth extracted
12. Number of non-measured target tooth/teeth extracted
13. Baseline tooth mobility

Site will be included as a random effect. The degrees of freedom will be adjusted by using Kenward Roger (KR) method. A Toeplitz structure (“type=toep”) will be specified as the covariance matrix. However, other covariance structures may be used in case of non-convergence. Covariates 8-12 will be assessed for adequacy in the model using a step-wise (backward) approach through the following algorithm.

1. Fit a full model using maximum likelihood with all covariates
2. Perform a likelihood ratio test for the full model and drop the covariate with the largest p-value for the likelihood ratio statistic if it is more than 0.05.
3. Drop one covariate (only covariates 7-14) and re-fit the model.
4. Perform a likelihood ratio test and drop the covariate with the largest p-value for the likelihood ratio statistic if it is more than 0.05.
5. Repeat steps 2 and 3 until no more covariates can be dropped.
6. Refit the final model with the covariates remaining in the model and estimate PD for each product use group using the restricted likelihood method.

Note that other covariates may be added if deemed necessary.

Number of subjects included in analysis, regression coefficients, 95% CI for regression coefficient, p-value for regression coefficient, Least Squares (LS) means (Cigarette User, IQOS User and Dual-User categories), Difference in LS Means (Cigarette User vs IQOS User/Dual-User) and 95% CI for Difference in LS Means will be presented.

The model fit will be assessed by the analysis of the residual (diagnostics) and by comparing the values predicted vs. the observed values (calibration).

Confidentiality Statement

Data and information contained in this document are considered to constitute trade secrets and confidential commercial information, and the legal protections provided to such trade secrets and confidential information are hereby claimed under the provisions of applicable law. No part of this document may be publicly disclosed without the written consent of Philip Morris Products S.A

Primary Analysis of Change from Baseline in PD at V4	
	The residuals, predicted vs observed values from the final model will be plotted.
Target visit	: V4 (6 Months)
Sample code	
ODS GRAPHICS ON;
 
PROC MIXED DATA = X METHOD=ML (REML for final model);
 
CLASS Product_use Subject Visit site;
 
MODEL PD reduction (Dependent variable) = avisit avisit*trt01a 3 4 5 6 7 8 9 10 11 12/ ddfm=kr outp=dsn residuals vciry;
 
RANDOM Site;
 
REPEATED / subject=visit (subject) type=toep;
 
LSMEANS Product_use * Visit / CL ALPHA=0.025 DIFF E UPPER;
 
RUN;
 
Where 1 2 3 4 5 6 7 8 9 10 11 12 refers to the covariates.
 
ODS GRAPHICS OFF;

Output	
15.4.5.1 Primary Analysis of Change from Baseline in Pocket Depth (mm) at V4 with Initial Pocket Depth \geq 4 mm - As Exposed Set -
 
15.4.5.2 Regression Coefficients and Graphical Diagnostics of Primary Analysis of Change from Baseline in Pocket Depth (mm) at V4 - As Exposed Set -
 
15.4.5.3 Primary Analysis of Change from Baseline in Pocket Depth (mm) at V4: Variables Dropped - As Exposed Set -

Summary Table of Mean full-mouth PD	
Population	: 
 • As Exposed Set 
 ➤ Product use pattern categories
Contents	: Refer to Descriptive statistics
Analysis	: 
 • Mean in full-mouth PD

Confidentiality Statement

Data and information contained in this document are considered to constitute trade secrets and confidential commercial information, and the legal protections provided to such trade secrets and confidential information are hereby claimed under the provisions of applicable law. No part of this document may be publicly disclosed without the written consent of Philip Morris Products S.A

variables	
 Change in mean full-mouth PD from baseline
Target visit	
 Baseline V3 (3 months) V4 (6 months)
Output	
15.2.5.1 Descriptive Statistics of Mean Full-mouth Pocket Depth (mm) and 95% CI - As Exposed Set -
 
15.2.5.2 Descriptive Statistics of Mean Pocket Depth (mm) in Subjects with Initial Pocket Depth ≥ 4 mm - As Exposed Set -
 
15.1.5.1 Plot of Full-Mouth Pocket Depth (mm) and 95% CI vs Visit by Product Use Categories - As Exposed Set -
 
15.1.7.1 Plot of Full-Mouth Pocket Depth (mm) and 95% CI vs Visit by Product Use Categories and Disease Severity - As Exposed Set -
 
15.1.7.2 Plot of Full-Mouth Pocket Depth (mm) and 95% CI vs Visit by Product Use Categories and Daily Cigarette Consumption - As Exposed Set -
 
15.1.7.3 Plot of Full-Mouth Pocket Depth (mm) and 95% CI vs Visit by Product Use Categories, Disease Severity and daily Cigarette Consumption - As Exposed Set -
 
15.1.7.4 Plot of Full-Mouth Pocket Depth (mm) and 95% CI vs Visit by Product Use Categories for Subjects with Initial Pocket Depth ≥ 4 mm - As Exposed Set -
 
15.3.5.1 Listing for Pocket Depth (mm) Value - As Exposed Set -
 
15.1.9.4 Plot of Mean Pocket Depth (mm) for Initial Sites with Pocket Depth ≥ 4 mm - As Exposed Set -

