## 12.6 Primary Analysis

The primary analysis evaluates the change from baseline in PD, which will be calculated for each patient across all sites with a baseline PD  $\geq 4$  mm, resulting in one value per patient per endpoint for each visit (baseline, Month 3 and 6).

The primary analysis will be performed on the As Exposed Set using a mixed model for repeated measurements (MMRM) for only subjects who have used cigarettes and/or Heatsticks. The model will include the PD change from baseline as the dependent variable, adjusting for daily cigarette consumption and disease severity at V1, full mouth PD at V1, exposure group and its interaction with visit. Site will be included as a random effect. The modeling assumptions will be evaluated and the model fit will be assessed by the analysis of the residual (diagnostics) and by comparing the values predicted vs. the observed values (calibration).

Additionally, the analysis will be performed on the FAS, PP and Adherent Use populations as a supportive sensitivity analysis. Additional sub group analyses such as for “Other” product use groups may be analyzed and will be defined in the SAP.

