3 STUDY OBJECTIVES AND ENDPOINTS

3.1 Primary Objectives and Endpoints

The primary objective of this study is:

To demonstrate the effect of switching to IQOS use compared to continued cigarette smoking on the response of pocket depth (PD) to mechanical periodontal therapy.

Endpoint (6 months):

Mean PD reduction in all sites with initial PD ≥ 4 mm after mechanical periodontal therapy.

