5 DERIVED AND COMPUTED VARIABLES

5.1 Dental/Clinical Assessments

5.1.1 Pocket Depth (PD)

PD is the distance from the gingival margin to which a probe penetrates into the pocket. Full mouth PD is measured based on 6 sites per tooth (6-site measurement method) at a pressure of approximately 20g using the intended probe at V1, V3 and V4. PD is recorded in 1 mm increments. If PD is not measurable on more than 2 sites, the whole tooth should be skipped and any periodontal parameters will not be measured for the tooth.

For each patient, Full mouth PD for a visit is calculated by the following formula which estimates the mean PD per tooth and then averages this for all teeth,

$$\text{Full Mouth PD (mm)} = \frac{1}{t} \sum_{i=1}^t \sum_{j=1}^{s_i} \frac{PD_{ij}}{s_i}$$

where PD_{ij} is the PD measurement of tooth i , $i = 1, \dots, t$ at the site j where $j = 1, \dots, s_i$. Note that s_i is the number of measurable sites per tooth and $s_i \geq 4$.

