9.5.2 Secondary Analyses

9.5.2.1 Secondary Analysis

Analysis of Change from Baseline in PD at V3 and CAL at V4 / V3	
Population	: • As Exposed Set
Contents	: The model will include the PD (or CAL) change from baseline as the dependent variable, adjusting for the following covariates; 
 • The statistical model is described in section 9.5.1. Note that “Full mouth PD at V1” will be replaced as “Full mouth CAL at V1”
Target visit	: • V3 (3 Months) for PD • V3 (3 Months) and V4 (6 Months) for CAL
Remarks	: • Statistical tests for PD at V3, CAL and V4 and V3 are performed in a sequential manner as detailed in section 9.1.8. • The same model for the primary analysis will be used with both V3 and V4 data included; PD at 3 months will be reported only if the test for PD between Cigarette User and IQOS User categories at 6 months is significant. • If the test between Cigarette User and IQOS Users Categories for PD is significant at V3, then the model with change from baseline CAL will be fitted with both V3 and V4 data and the test between CC and IQOS for CAL at V4 will be reported. • If the test between Cigarette User and IQOS User categories for CAL at V4 is significant, then the test between Cigarette User and IQOS User Categories for CAL at V3 will be reported.
Sample code	Refer to “ Primary Analysis ”
Output	15.4.7.1 Analysis of Change from Baseline in Pocket Depth (mm) at V3 with Initial Pocket Depth \geq 4 mm - As Exposed Set - 15.4.7.2 Regression Coefficients and Graphical Diagnostics of Analysis of Change from Baseline in Pocket Depth (mm) at V3- As Exposed Set - 15.4.7.3 Analysis of Change from Baseline in Clinical Attachment Level (mm) with Initial Pocket Depth \geq 4 mm - As Exposed Set -

Confidentiality Statement

Data and information contained in this document are considered to constitute trade secrets and confidential commercial information, and the legal protections provided to such trade secrets and confidential information are hereby claimed under the provisions of applicable law. No part of this document may be publicly disclosed without the written consent of Philip Morris Products S.A

Analysis of Change from Baseline in PD at V3 and CAL at V4 / V3

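### The PD and CAL models leave out the endpoint's own baseline; for PD this costs something only in the ≥ 5 mm severity stratum, for CAL in both strata

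*SAP*

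**What the plan says.** SAP 3.1 defines the primary endpoint as "Mean PD reduction in all sites with initial PD" of 4 mm or more, at six months. Protocol 12.6 turns this into a patient-level mean, "resulting in one value per patient per endpoint for each visit", and fits a mixed model "adjusting for daily cigarette consumption and disease severity at V1, full mouth PD at V1, exposure group and its interaction with visit".

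SAP 9.5.1.1 carries these terms over as "2. Disease severity at V1" and "3. Full mouth PD at V1". Full-mouth PD comes from a formula "which estimates the mean PD per tooth and then averages this for all teeth" (SAP 5.1.1), so shallow sites count as much as deep ones. Mean V1 PD over the endpoint sites is not among the 13 listed covariates. Severity and full-mouth PD lie outside both ranges that the SAP gives for backward selection (8 to 12 in one place, 7 to 14 in another), so both stay in the model.

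For CAL, SAP 9.5.2.1 swaps in "Full mouth CAL at V1". By contrast, the urinary biomarker model (9.5.2.1) and the gingival fluid model (9.5.3) each include the baseline of their own outcome. The primary contrast is between product-use groups in the As Exposed Set (SAP 8.1, 9.5.1.1), not between randomized arms.

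**The concern.** Change from baseline usually depends on where it started, through regression to the mean and because deeper pockets have more room to heal. The protocol accepts this: section 4.1 justifies stratifying on PD by the influence of pre-treatment depth on the response to therapy. The natural adjustment is therefore the V1 value of the quantity whose change is analysed.

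Full-mouth PD is a different quantity. It mixes how many sites are deep with how deep they are. A binary severity term adds only whether the single worst site reaches 5 mm. If patients alike on both terms still differ in endpoint baseline, two things follow. Residual variance is larger than it need be. And because the groups are formed by what patients chose to use, a difference in endpoint baseline between them is not limited to chance and is only partly removed.

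**Working it through.** **1. The plan's own figure.** Protocol 12.2 gives one-sided alpha 2.5%, power 80%, SD 0.5 mm and difference 0.25 mm.

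n per group = 2 × (1.960 + 0.842)² × 0.5² / 0.25² = 62.8, so 63 by the normal approximation. The two-sample t calculation needs 64 (power 80.1% at 64, 79.5% at 63). Then 64 / (1 − 0.25) = 85.3, so 86 per arm and 172 in total. The figure reproduces. It uses SD 0.5 with no explicit allowance for covariates.

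**2. Where the endpoint baseline can vary.** PD is recorded in 1 mm steps (SAP 5.1.1), and severity is set by the deepest site (SAP 4.1).

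- In the < 5 mm stratum every qualifying site is at least 4 mm and below 5 mm, hence exactly 4 mm. The endpoint baseline is 4.0 mm for every patient, and the severity term captures it fully.
- In the ≥ 5 mm stratum it can take any value above 4 mm.

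The quota puts at least 50% of randomized patients in the ≥ 5 mm stratum. If the cap of 80 on the < 5 mm stratum is study-wide, that stratum holds at most 80/172 = 46.5%, leaving at least 92/172 = 53.5% in the other.

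**3. How far apart two matched patients can be.** Take two mouths of 20 teeth with all 120 sites measured. The mean of tooth means then equals the site mean.

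| Mouth | Sites | Full-mouth PD | Deepest site | Mean over sites ≥ 4 mm |
|---|---|---|---|---|
| A | 40 at 5 mm, 80 at 2 mm | 360/120 = 3.00 | 5 mm | 200/40 = 5.00 |
| B | 56 at 4 mm, 2 at 6 mm, 62 at 2 mm | 360/120 = 3.00 | 6 mm | 236/58 = 4.07 |

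Both fall in the ≥ 5 mm stratum. Covariates 2 and 3 treat them as identical, yet their endpoint baselines differ by 0.93 mm.

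**4. CAL.** Protocol 2.1 gives CAL as PD plus gingival recession. Recession varies even where PD is exactly 4 mm, so mean V1 CAL over the endpoint sites varies in both strata, and the severity term does not fix it in either.

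**5. Precision, on assumed values.** Take SD 0.5 as the residual SD under the current model. Let w be the share of patients in the ≥ 5 mm stratum, and p the extra partial R-squared there from the endpoint's own baseline. Then SD = 0.5 × √(1 − w·p), and power = Φ(0.25 / (SD × √(2/64)) − 1.96). With p = 0 this is 80.7%. With w = 92/172:

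| p | SD | Power at 64 per group | n per group for 80% | CI narrower by |
|---|---|---|---|---|
| 2% | 0.497 | 81.2% | 63 | 0.5% |
| 5% | 0.493 | 81.8% | 62 | 1.3% |
| 10% | 0.486 | 82.8% | 60 | 2.7% |
| 20% | 0.473 | 84.9% | 57 | 5.5% |

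Over the same range of p, w = 0.5 gives 81.1% to 84.6%, and w = 1 gives 81.5% to 88.5%.

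**6. Bias, on assumed values.** Shift in the contrast = slope of change on own baseline × the group difference in own baseline that remains after adjusting for full-mouth PD and severity. Slopes of 0.2 to 0.5 mm per mm with remaining differences of 0.05 to 0.2 mm would give 0.01 to 0.10 mm. The documents supply neither input.

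**The case against.** The severity term does much of the work. It removes the PD problem in the < 5 mm stratum and, with full-mouth PD, reduces it in the other. This stands, and it is why the PD point is confined to the ≥ 5 mm stratum. A reader might infer that every patient's PD adjustment is deficient; the whole-millimetre recording rules that out.

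Selection may also be mild. The plan assumes 10% non-adherence (SAP 6). If 10% leave one group, the mean of those who stay shifts by 0.1 times the leaver–stayer difference, so a shift of 0.1 to 0.2 mm needs a difference of 1 to 2 mm in endpoint baseline. The Full Analysis Set, analysed by randomized product, gives a supportive check. This also stands. A reader might take the 0.10 mm at the top of step 6, or 40% of the planned 0.25 mm, as the bias of the planned analysis. The documents do not support that: nothing in them says what imbalance remains after the planned adjustment.

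Finally, SAP 9.5.1.1 leaves room for further covariates and requires residual and calibration checks. That is weaker as a defence. An optional later addition is not a pre-specified covariate, and this one is prognostic by the protocol's own reasoning.

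**Conclusion.** The mismatch is certain from the text of both documents. The adjustment omits the endpoint's own baseline, although the SAP uses own baselines in its biomarker and gingival fluid models. For PD it has no effect in the < 5 mm stratum and leaves avoidable variance and some avoidable imbalance in the ≥ 5 mm stratum. For CAL it applies in both strata.

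Its size cannot be derived from the documents. Under the stated assumptions (extra partial R-squared 2% to 20%, 92 of 172 patients affected, SD 0.5 as the current residual SD) the gain in power is roughly half a point to four points. No size was calculated for CAL, and no credible figure for the remaining bias can be given.

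A reader might also infer that the trial is underpowered. It is not shown to be: 64, 86 and 172 all reproduce, and the calculation claims no covariate gain. The case for changing the plan is that the improvement is almost free and reduces one avoidable source of imbalance in a non-randomized contrast. It does not remove other confounding from self-selected product use.

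**What to change.** - In SAP 5.1, add a derivation of mean V1 PD and mean V1 CAL over sites with initial PD of 4 mm or more. Section 5.1 has no such formula now. Use the same site or tooth weighting as the endpoint.
- In SAP 9.5.1.1, add mean V1 PD over those sites as a covariate, and state that it is forced in and outside the backward selection. Do not simply append it as number 14, because one step of the selection algorithm names covariates 7 to 14 as droppable. Full-mouth PD may stay. Add the term to the sample code.
- In SAP 9.5.2.1, use the same PD model for V3, and add mean V1 CAL over those sites to the CAL model on the same terms.
- Record the change in SAP section 7, since protocol 12.6 names the covariates.

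The cost is a few lines of SAP text and one degree of freedom per model. Every site value is already recorded at V1, so no new data are needed. The change should be made while the statisticians are still blinded to post-randomization PD and CAL.
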